3 STUDY DEVICE

3.1 Device Description

The VCool Intranasal Cooling System is intended to cool the core body temperature of patients for whom cooling is medically indicated. The VCool System produces a flow of thermoelectrically cooled air from an external source (hospital compressed wall medical air or oxygen). The air flow is delivered from the VCool System to the patient via an insulated air delivery tube. The air delivery tube is insulated to keep the air cooled. A two-prong nasal cannula is attached to the delivery tube and placed in the patient's nostrils. Cooled air enters the nasal passages and exits freely through the nose and mouth. The nasal prongs do not create a seal at the nostrils and therefore do not create excess airway pressure. The VCool System does not utilize invasive catheters, surface cooling pads, or any cooling agents. The VCool System is not used to deliver respiratory support.

The VCool is a small device weighing less than 25 pounds. There is an internal power source, a Peltier (thermoelectric cooling unit), air tubing, and thermistors. The system can deliver air flow rates of up to 40 liters per minute set to a temperature of 5°C at the end of the cannula. All parts of the system are constructed of biocompatible materials and designed for electrical safety. In this study, the VCool will be connected to a medical grade air compressor which will supply the air for cooling. A commercially available nasal cannula will be used to deliver the cooled air.

3.2 Indications for Use

The VCool Intranasal Cooling System is intended for temperature reduction in adult patients where cooling is medically indicated.

4 INVESTIGATIONAL PLAN

4.1 Study Design

This is a single-center, prospective, open label, feasibility study in healthy adult participants. Eligible participants who have signed an informed consent will be enrolled in the study. The participant will be assigned a unique ID number. After obtaining relevant demographic information, testing will ensue.

Baseline vital sign measurement (heart rate, temperature, blood pressure, respiratory rate) will be obtained. The participant will then undergo continuous MRI of the brain to include sequences that enable thermography. Baseline imaging sequences will take approximately 30 minutes. The investigator or designee will turn on the VCool System, while the VCool remains outside of the MRI suite, for up to two hours or until the target temperature of 35.5°C is reached. Body temperature will be continuously measured using a MRI compatible thermometer. During the cooling period and once endpoint is reached the participant will undergo repeated MRI with thermography. Once study endpoint is reached, the participant will be taken off of VCool and MRI thermography. If the target core body temperature is reached before 2 hours, the participant will be monitored until two hours are completed to determine if the VCool System can maintain the participant's core body temperature between 35°C and 36°C for one hour.

During the study, the participants will have their temperature monitored and will be assessed for shivering and adverse events.

Study participation is one visit lasting approximately 4 hours.

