1 PROTOCOL SYNOPSIS

Protocol Title:	Feasibility Study for VCool Intranasal Cooling System in Healthy Volunteers
Protocol Number:	00080424
Version:	2.0
Date:	01 August 2024
Development Phase:	Pilot Study
Sponsor:	NeuroIntact, Inc. [name]
Study Objective:	The objective of this study is to evaluate the performance and safety of the VCool Intranasal Cooling System in healthy adult volunteers. The study is designed to gather preliminary data regarding air flow rates and time required to reduce core body temperature to 35.5°C and maintain the temperature between 35°C and 36°C for one hour after cooling.
Number of Sites / Number of Participants:	The study will be conducted at one site in Maryland. A total of 10 participants need to complete the study.
Primary Endpoints:	
1. To confirm the VCool System can lower core body temperature to 35.5°C within 2 hours.2. To confirm the VCool System can maintain a core body temperature between 35°C and 36°C for one hour after cooling.3. To demonstrate the differential impact of VCOOL system between core body and brain temperature
Secondary Endpoint:	
1. To assess the shivering experienced by participants based on the 4-point Bedside Shivering Assessment Scale (BSAS).
Safety Evaluation:	All treatment emergent adverse events (TEAEs) reported by participants will be tabulated. Each adverse event (AE) will be evaluated by the Investigator in terms of seriousness, severity (mild, moderate, severe) and relationship (not related, possibly related, probably related, definitely related) to the study device.
Study Design:	This is a single-center, prospective, open label, feasibility study in healthy adult participants. Participants will be monitored for up to 2 hours while using the VCool System to determine if the target temperature of 35.5°C is reached. If the target core body temperature is reached within 2 hours, the participant will be monitored for an additional hour to determine if the VCool System can maintain the participant's core body temperature between 35°C and 36°C for one hour.

	During the study, the participants will have their blood pressure and temperature monitored and will be assessed for shivering and adverse events.
Study Duration:	The overall study participation for each participant will be one visit lasting approximately 4 hours. Study enrollment is anticipated to be completed within two weeks.

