5 STUDY ENDPOINTS

5.1 Primary Endpoints

1. To confirm the VCool System can lower core body temperature to 35.5°C within 2 hours.
2. To identify whether cooling with the VCool System results in a gradient between brain and core body temperature.
3. To confirm the VCool System can maintain a core body temperature between 35°C and 36°C for one hour after cooling.

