7.6 Procedure

7.6.1 **VCool System Set Up**

Attach the disposable delivery tube to the VCool System

Install the gas inlet filter on the back with the filter bowl vertical (glass side down)

Attach the air hose to the gas inlet filter

Connect the power cord to a grounded outlet

Turn the power switch to "ON"

Connect the RS232 cable to the VCool System and to the laptop computer

Turn on the computer

Select the following:

TC-48-20 program.

COM5

Communications

Set Point and set value to -19.0

Controller options

Save data to file

Go to file Explorer, select LabView Data

Select New and enter participant identification number as file name

Save data to file

Turn on gas and set flow meter to 35 liters per minute.

Confirm temperature is set to -10°C

Confirm gas temperature setting at the end of the delivery tube is -5°C

Attach nasal cannula to the delivery tube

7.6.2 *MR Imaging procedure*

- Participants will undergo MRI at the HSF3 research facility at the University of Maryland, Baltimore (UIMB). Each imaging session will last approximately 90 minutes. The protocol will include high-resolution anatomical MRI for structural reference and tissue segmentation; MR Spectroscopy (MRS) to measure metabolite and water resonance frequencies for temperature estimation; MR Thermometry to measure phase changes over time to track temperature dynamics; Perfusion MRI to measure cerebral blood flow (CBF); as well as other structural and functional imaging sequences. These sequences will be repeated at multiple time points during the controlled cooling period to monitor temporal changes in temperature, perfusion, and tissue properties.

7.6.3 *Participant Set Up and Monitoring*

Have the participant lie on their back in an inclined position and place the nasal cannula on the participant, securing the straps around their head

Record the temperature from both temperature sensors and record the time

Record the flow rate

Initiate the cooling and record the time. The induction phase for participant cooling can take up to 2 hours.

Record the core body temperature every 2 minutes from both temperature sensors and record the time. The core body temperature is monitored throughout the study.

If the core body temperature is <35°C for 5 minutes:

1. Remove nasal cannula, if temperature starts to rise after 2 minutes keep cannula off until temperature gets back to 35°C. Then reapply nasal cannula and resume treatment.

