2. If temperature continues to fall below 35°C after 2 minutes, cover patient with electric blanket that has been pre heated on standby. Keep blanket on until temperature gets back to 35°C.

Assess for shivering every 10 minutes using the BSAS. Record the results and time. The BSAS is recorded throughout the study.

Bedside Shivering Assessment Scale

0	None
1	Mild: Shivering localized to neck/thorax
2	Moderate: Intermittent involvement of the upper extremities and/or thorax
3	Severe: Generalized shivering or sustained upper and/or lower extremity shivering

The flow can be increased to 40 liters per minute after 10 minutes

Record any VCool System adjustments to flow rate or temperature and record the new flow rate and temperature and time of adjustment. Record the reason for the adjustment.

Assess the participant for adverse events (AEs) throughout the study

If the participant has a nosebleed, discontinue the study and note the time.

Monitor patient at first sign of shivering

- If **Mild**, cover patient with regular blanket.
- If **Moderate or severe** – discontinue cooling treatment.

Continue to record the temperature until either temperature sensor reaches 35.5°C or the VCool System has been used for 2 hours. Note the time the target temperature was achieved.

If the participant's core body temperature does not reach 35.5°C in 2 hours, the study is concluded

- Remove the nasal cannula from the participant and dispose of it properly
- Monitor the participant's core body temperature until it returns to baseline. Blankets can be applied to help with warming.
- Remove the axillary thermometer

If the participant's core body temperature reaches 35.5°C, proceed to the next steps

Maintain the target temperature of 35.0°C to 36.0°C for 1 hour:

Adjust flow rate by 5 liters per minute from baseline every 2 minutes

- If temperature falls below 35°C., reduce flow rate by 5 liters per minute every 2 minutes until temperature rises back to 35°C
- If temperature rises above 36°C, increase flowrate 5 liters per minute every 2 minutes until temp falls below 36°C

Remove the nasal cannula and the air delivery tube and dispose of them properly

Once out of the MRI suite, record the patient temperature (°C) using the 3M SpotOn® zero-heat-flux forehead sensor, the Braun ThermoScan 7 tympanic sensor

Monitor the participant's core body temperature until it returns to baseline. Blankets can be applied to help with warming.

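### Section 4.1 ends maintenance monitoring at two hours of cooling, so anyone reaching 35.5°C after minute 60 gets less than the one hour that a primary endpoint requires

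*Protocol*

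**What the plan says.** Section 4.1 (Study Design) runs VCool "for up to two hours or until the target temperature of 35.5°C is reached". It then says "Once study endpoint is reached, the participant will be taken off of VCool and MRI thermography", without defining that endpoint. The next sentence sets the follow-on period: "If the target core body temperature is reached before 2 hours, the participant will be monitored until two hours are completed". The same sentence gives the purpose of this monitoring as judging whether the system can hold 35–36°C for one hour.

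Three other places bear on the same period:

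- **Section 5.1, primary endpoint 3:** "To confirm the VCool System can maintain a core body temperature between 35°C and 36°C for one hour after cooling".
- **Synopsis, Study Design:** if the target is reached within 2 hours, "the participant will be monitored for an additional hour to determine if the VCool System can maintain" the 35–36°C range for one hour.
- **Section 7.6.3:** up to 2 hours to reach target, then "Maintain the target temperature of 35.0°C to 36.0°C for 1 hour" with flow changed in steps of 5 L/min, and only then "Remove the nasal cannula and the air delivery tube and dispose of them properly".

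Section 12.1 bases the primary analysis on the time and flow rate needed both to reach and to hold the target, which presumes that the device is running during maintenance.

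**The concern.** The cut-off in Section 4.1 is fixed to the start of cooling, whereas the endpoint it serves is fixed to the time the target is reached. The later a participant reaches target, the shorter the maintenance window. A participant can meet the cooling endpoint in full and still have no complete hour on which to judge maintenance.

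Device status is a second, less certain problem. If the undefined study endpoint in Section 4.1 means reaching 35.5°C, VCool comes off at that moment, later readings show passive rewarming, and maintenance by the device is tested in no one. If it means the end of the study, only the window conflict remains.

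With 10 completers planned, each participant without a full hour is one tenth of the data on a primary endpoint.

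**Working it through.** **Inputs**

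- Longest cooling time to target: 120 min (Sections 4.1, 5.1 and 7.6.3).
- End of maintenance monitoring: minute 120 (Section 4.1); t + 60 (synopsis and Section 7.6.3).
- Required maintenance: 60 min (Section 5.1).
- Reading interval: 2 min (Section 7.6.3: "Record the core body temperature every 2 minutes from both temperature sensors").
- Baseline core temperature: 36.8–37.5°C (Section 6.1).
- Baseline imaging about 30 min; visit about 4 h, i.e. 240 min (Section 4.1).

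**Window available under Section 4.1**

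Window = 120 − t. Reading intervals = (120 − t) / 2.

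| Time to target t (min) | Window, Section 4.1 (min) | Reading intervals | Window, synopsis and 7.6.3 (min) |
|---|---|---|---|
| 30 | 90 | 45 | 60 |
| 60 | 60 | 30 | 60 |
| 75 | 45 | 22.5 | 60 |
| 90 | 30 | 15 | 60 |
| 105 | 15 | 7.5 | 60 |
| 120 | 0 | 0 | 60 |

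Setting 120 − t ≥ 60 gives t ≤ 60. The one-hour figure in the endpoint is therefore available under Section 4.1 only to those who reach target in the first hour. For t below 60, Section 4.1 gives more than an hour, which also differs from the other two places.

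**Cooling rate implied**

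- Required fall: 36.8 − 35.5 = 1.3°C up to 37.5 − 35.5 = 2.0°C.
- Target by minute 120 (cooling endpoint): 1.3/2 to 2.0/2 = 0.65–1.0°C/h.
- Target by minute 60 (full hour under Section 4.1): 1.3–2.0°C/h.

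Followed literally, Section 4.1 asks for cooling twice as fast as the cooling endpoint does before maintenance can be fully assessed.

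**Schedule with a full hour after target**

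- Latest end of VCool use: 120 + 60 = 180 min.
- Longest path including baseline imaging: 30 + 120 + 60 = 210 min.
- Left in the visit: 240 − 210 = 30 min.

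**The case against.** The strongest reply is that the operating text is sound. Section 7.6.3 is the step-by-step procedure, it gives a full hour with flow adjustment, and the synopsis and endpoint agree with it. Even the sentence in Section 4.1 names one hour as its purpose. Staff who work from Section 7.6.3 would collect the right data. This is fair as a forecast of conduct, but the protocol has no rule saying which section prevails, and Section 4.1 is the one headed Study Design. That its sentence names one hour shows only that its cut-off fails its own purpose. An analysis plan cannot settle the matter either, because it cannot supply a maintenance hour that was never delivered.

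The device-off reading is open to challenge. Monitoring to see whether the system can maintain temperature makes little sense with the system off, and Section 4.1 also has MRI repeated once the endpoint is reached. This stands as a reason to treat device status as an ambiguity to be removed, not as an established error.

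It is also true that temperatures are recorded after the study period, since Section 7.6.3 monitors until return to baseline. Under that section, however, those readings follow cannula removal and cannot show maintenance by the device.

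Finally, Section 7.6.2 puts an imaging session at about 90 minutes, and a full hour for late reachers exceeds that. But 30 minutes of baseline plus up to 120 of cooling is already 150 minutes, and Section 7.6.3 has the participant leave the MRI suite only after the maintenance hour. Aligning Section 4.1 adds no scanner time beyond what Section 7.6.3 already requires.

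**Conclusion.** The concern holds. As written, Section 4.1 gives less than the required hour to anyone reaching 35.5°C after minute 60 and up to minute 120, and it contradicts the synopsis and Section 7.6.3. The shortfall is t − 60 minutes, from just above zero to the whole hour. Because it affects a primary endpoint, it must be corrected.

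The conclusion assumes that the two hours in Section 4.1 run from the start of VCool, which is the natural reading given the cooling limit in the same paragraph. Counting two hours from target would fit neither the synopsis nor the stated one-hour purpose. Confidence is high on the window conflict and moderate on the reading that the device is off after target. The number of participants affected is unknown and could be zero if all cool within the first hour.

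**What to change.** Amend Section 4.1 to match the synopsis and Section 7.6.3, for example:

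> If core temperature reaches 35.5°C at any time within 2 hours of cooling, VCool continues, with flow adjusted per Section 7.6.3, for 60 minutes from the recorded time of target attainment (no later than minute 180 of cooling).

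Replace the undefined study endpoint with the event that ends device use: the end of that hour, or minute 120 if the target is not reached. The early-stop rules in Section 7.6.3 are unchanged. That section already has staff note when the target was reached, so no new data item is needed. The amendment should also say which sensor starts the hour, because Section 7.6.3 accepts either of two sensors while Section 7.5 removes the forehead and tympanic sensors before MRI.

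The cost is a wording change to one paragraph, plus device and room time for late reachers that the synopsis and Section 7.6.3 already imply. The roughly 30 minutes left on the longest path must cover consent, set-up and rewarming, so such a visit may run somewhat past 4 hours. The stated visit length should allow for this.

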4.2 Study Site

The study will be conducted at the University of Maryland School of Medicine HSF III research facility.

4.3 Participant Enrollment

Participants will be screened for inclusion in the study to ensure that 10 participants complete the study.

5 STUDY ENDPOINTS

5.1 Primary Endpoints

1. To confirm the VCool System can lower core body temperature to 35.5°C within 2 hours.
2. To identify whether cooling with the VCool System results in a gradient between brain and core body temperature.
3. To confirm the VCool System can maintain a core body temperature between 35°C and 36°C for one hour after cooling.

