2.2 Study Objective

The objective of this study is to evaluate the performance and safety of the VCool Intranasal Cooling System (VCool) in healthy adult volunteers. The study is designed to gather preliminary data regarding air flow rates and time required to reduce core body temperature to 35.5°C and maintain the temperature between 35°C and 36°C for one hour after cooling. Additional data will be obtained on whether intranasal cooling results has a differential temperature impact on core body temperature as compared to brain temperature.

The data collected will help to develop automated cooling models and the control system algorithm by examining participant cooling response as a function of air flow rate and time the air is supplied to the participants.

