7.3 Study Enrollment

7.3.1 *Participant Identification*

If the volunteer is willing to participate in the study and has signed and dated the ICF, they will be assigned a unique ID number. The ID number is a 2-digit number assigned sequentially (i.e., 01, 02, 03). The ID number will be written on each page of the CRF, and all other documents related to the participant.

The site will maintain a screening and enrollment log for participant identification, to which all consented participants will be added. A participant is considered enrolled when they have signed the ICF. If during the screening process a participant fails to fulfill any of the eligibility criteria, this will be documented, and the participant will be classified as a screen failure. Volunteers will continue to be screened until 10 participants have completed the study.

The Principal Investigator (PI) or designee at each site will maintain a master log that will correlate each participant ID number to the participant's name. The log will remain with the PI and will be confidential.

7.3.2 *Participant Stipend*

Participants will be issued a stipend of 200\$ for their participation in the study.

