12 DATA ANALYSIS

12.1 Primary Analysis

The time and flow rate that is required to reduce and maintain each participant's core temperature to 35.5°C from measured baseline temperature will be calculated. The total number of participants who reach the target temperature in 2 hours or less will be calculated.

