12.3 Populations for Analysis

The study population will consist of 10 healthy volunteers who have signed the ICF and who meet all the inclusion criteria and none of the exclusion criteria.

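### Two primary endpoints claim to 'confirm' reaching and holding target temperature, but the protocol sets no success criterion, has no participant count for the hold, and leaves the denominator open to replacement

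*Protocol*

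**What the plan says.** - **Endpoints.** Protocol 5.1 lists as endpoint 1 "To confirm the VCool System can lower core body temperature to 35.5°C within 2 hours" and as endpoint 3 "To confirm the VCool System can maintain a core body temperature between 35°C and 36°C for one hour after cooling". The synopsis carries the same two as its endpoints 1 and 2. Neither states how many participants, or what proportion, must succeed.
- **Objective.** Section 2.2 describes a different kind of study: "The study is designed to gather preliminary data regarding air flow rates and time required to reduce core body temperature". The synopsis and 4.1 call it a feasibility study.
- **Analysis.** Section 12.1 has two parts. The first is per participant: "The time and flow rate that is required to reduce and maintain each participant's core temperature to 35.5°C". The second is a count: "The total number of participants who reach the target temperature in 2 hours or less will be calculated". No count is defined for staying within 35-36°C for one hour.
- **Who is counted.** The synopsis says "A total of 10 participants need to complete the study". Section 7.3.1 adds: "Volunteers will continue to be screened until 10 participants have completed the study". Section 12.3 then fixes the analysis set: "The study population will consist of 10 healthy volunteers who have signed the ICF", subject to the eligibility criteria.

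**The concern.** An endpoint that is to be confirmed needs a result that would fail to confirm it. The protocol provides none. Read literally, a claim that the system *can* lower temperature is met by one responder, so 1, 5 and 10 successes out of 10 could all carry the same conclusion. The hold endpoint is less well served, because 12.1 does not even define the participant-level result to be counted.

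The denominator adds to this. Section 7.6.3 provides for stopping the study or the cooling after certain events, and section 8 allows withdrawal. If such participants do not count as having completed, they can be replaced until 10 have. The reported figure would then describe those who tolerated the procedure, not those who started it.

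At stake is what the trial may be said to have shown. The data collected would be the same either way.

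**Working it through.** **Is there a figure to reproduce?** No. The protocol gives N = 10 without a reference rate, target rate, error rate or precision. The calculations below only size the consequence. True success rates and numbers of replaced participants are assumptions, shown as ranges.

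**Step 1: the loosest reading of 'can'.** The chance of at least one success in 10 at true rate p is 1 − (1 − p)^10.

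| Assumed true rate p | Chance of at least 1 of 10 |
|---|---|
| 5% | 1 − 0.95^10 = 40.1% |
| 10% | 1 − 0.90^10 = 65.1% |
| 20% | 1 − 0.80^10 = 89.3% |
| 30% | 1 − 0.70^10 = 97.2% |

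**Step 2: what each count supports.** Exact (Clopper-Pearson) two-sided 95% limits for x of n are the 2.5% quantile of Beta(x, n − x + 1) and the 97.5% quantile of Beta(x + 1, n − x). When x = n the lower limit reduces to 0.025^(1/n).

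| Result | Exact 95% interval |
|---|---|
| 1/10 | 0.3% to 44.5% |
| 5/10 | 18.7% to 81.3% |
| 8/10 | 44.4% to 97.5% |
| 10/10 | 69.2% to 100% (lower limit 0.025^(1/10) = 0.692) |

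**Step 3: the hold endpoint.** Under 7.6.3 only participants who reach 35.5°C go on to the hold hour. Among m entrants who all hold, the lower limit is 0.025^(1/m):

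- m = 7: 59.0%
- m = 5: 47.8%
- m = 3: 29.2%

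If all 10 reach target, the precision is that of step 2.

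**Step 4: the denominator.** Put three places side by side.

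- Section 7.3.1 continues until 10 complete, and 'completed' is not defined.
- Section 7.6.3 ends the study for a participant who has not reached 35.5°C at 2 hours. That person can fairly be called a completer and a failure. The same section also provides for earlier stops, whose status is not given.
- Section 12.3 admits eligible, consented volunteers but fixes their number at 10. If k eligible participants are stopped early and replaced, 10 + k people meet its description, and k of them must be left out to keep the number at 10.

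Take 10 successes among 10 completers, with k early stops replaced and all of them stopped before reaching target:

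| Assumed k | Completers only | All in whom cooling started | Exact 95% interval, all started |
|---|---|---|---|
| 0 | 10/10 = 100% | 10/10 = 100% | 69.2% to 100% |
| 1 | 10/10 = 100% | 10/11 = 90.9% | 58.7% to 99.8% |
| 2 | 10/10 = 100% | 10/12 = 83.3% | 51.6% to 97.9% |
| 3 | 10/10 = 100% | 10/13 = 76.9% | 46.2% to 95.0% |

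**The case against.** **This is a first-in-use feasibility study, and 'confirm' is an ordinary verb.** The protocol states no hypothesis, error rate or power, so the word may mean only a check of capability. A single-arm feasibility study does not need a success rule. This stands in part: a descriptive analysis of 10 participants is acceptable, and nothing here calls for a test or a larger sample. But the verb sits in the primary endpoints, and the protocol's own objective and analysis do not support it.

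**The count will be visible.** A reader shown 1/10 will see 1/10. The stated use of the data in 2.2 is to develop cooling models and a control algorithm, and no go/no-go decision or later sample size is tied to the count. This is fair and limits the harm to the conclusion drawn. It does not help with the hold, for which no count is defined, or with early stops that may be left out.

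**Stronger readings the document does not support.**

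- *The primary analysis is only a count.* It is not: 12.1 also derives time and flow rate per participant, which match the objective. They supply no criterion, however.
- *Any result at all would confirm.* Zero of 10 could not be presented that way; the point is limited to non-zero counts.
- *The missing confidence interval is itself a defect.* An analysis plan may exist that supplies one. The interval belongs to the remedy.
- *Early stops will be excluded.* The protocol does not say so. It leaves the possibility open.

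**Conclusion.** The point holds as a mismatch between claim and analysis. Two primary endpoints are worded as confirmation, while the objective is preliminary data and the analysis is descriptive, with no success criterion and no participant-level count for the hold. An analysis plan could add an interval but would inherit the endpoint wording.

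In size: a single responder meets the loosest reading, and that would occur with probability 65% at an assumed true rate of 10% (40% at 5%, 89% at 20%). The best possible result, 10/10, excludes only rates below about 69%. For the hold, 5 of 5 would exclude only rates below about 48%. If one to three early stops were replaced and left out, a reported 100% would correspond to 91% down to 77% of those started.

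These figures assume independent participants with a common success rate. The last range also assumes that stopped participants do not count as completers and had not reached target. The change is worth making before data are seen, but it does not call the design into question.

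**What to change.** 1. **Synopsis and 5.1.** Replace 'confirm' in the two endpoints with: estimate the proportion of participants in whom cooling is started who reach 35.5°C within 2 hours; and, likewise, who hold 35-36°C for one hour. Show the hold proportion also among those who reached target.
2. **Section 12.1.** Report n/N with exact 95% intervals for both endpoints, beside the time and flow-rate descriptions already planned. State that a participant whose cooling stops before 35.5°C is reached counts as not reaching target.
3. **Sections 7.3.1 and 12.3.** Say that everyone in whom cooling is started stays in this denominator, even if recruitment continues until 10 complete.

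If the sponsor prefers to keep 'confirm', it would have to prespecify a minimum number of successes for each endpoint and give its operating characteristics. For example, at least 8 of 10 has a one-sided error of 0.055 at an assumed true rate of 50% and power of 0.68 at an assumed 80%.

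**Cost.** A few lines of text, with no new procedures and no change to the recruitment target. The claim becomes less favourable, and the denominator may exceed 10.
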